**6.4 Select the methods used to recruit individuals.**

 Email	 Screening of the Electronic Medical Record (EMR)
--------------------------------	--

# IRB Protocol for Human Subjects

## Research

 Face to face	 Social media
 Flyers	 SONA System
 In person presentations	 TV, Radio, Print
 Online advertisements	 Other – please explain: Click or tap here to enter text.
 Phone calls	

**6.5 Explain the recruitment process. Describe how potential subjects will be identified, where recruitment will take place, when recruitment will occur, and the methods that will be used to recruit individuals.**

Subjects will be identified by the study investigators who are BUMCP physician medical toxicologists and care for RSEs at BUMCP. Subjects will be screened and interviewed using the inclusion/exclusion criteria and if eligible, be asked if they would like to participate in the study. The informed consent form will be reviewed by a trained investigator with the subject/legally authorized representative. To include the voluntary nature of the study, risks/benefits, and study procedures will be explained in detail. Adequate time to review the informed consent form will be given and all questions and concerns will be addressed. The subject/legally authorized representative be given a copy of a signed consent if they choose to participate.

### 7.0 Consenting Process:

**7.1 Indicate the informed consent process(es) and/or document(s) for the study. Check all that apply.**

Written Consent
 Informed Consent (ICF) – written or electronically signed form
 Parental Permission – written or electronically signed form
 Assent (participants under 18) – written or electronically signed form
 Combined ICF/PHI Authorization – written or electronically signed form
 Protected Health Information (PHI) Authorization – written or electronically signed
 Translated Consent/Assent – written or electronically signed form(s)
 Short Consent Form – written or electronically signed form (see guidance on Short Form process )
 Debriefing Script or Form – document used to properly inform subjects of the study's purpose when intentionally deceived

# IRB Protocol for Human Subjects Research

## Oral/Online/Unsigned Consent (Appendix for Alteration/Waiver of Consent or PHI is Required)

 Informed Consent – oral script/online/unsigned
 Parental Permission – oral script/online/unsigned
 Assent – oral script/online/unsigned
 Translated Consent/Assent – oral script/online/unsigned

## Waivers of Informed Consent and/or PHI Authorization

 Waiver of Consent
 Full Waiver of PHI Authorization
 Partial Waiver of PHI for Screening Purposes

**7.2 Describe in detail the consent processes checked above, including any waiting period for subjects to sign the consent, steps to minimize the possibility of coercion or undue influence, and the language used by those obtaining consent.**

The informed consent form will be reviewed by a trained investigator with the subject/legally authorized representative. To include the voluntary nature of the study, risks/benefits, and study procedures will be explained in detail. Adequate time to review the informed consent will be given, all questions and concerns will be addressed. If the subject/legally authorized representative choose to participate they will be asked to sign the paper informed consent form and will be given a copy of the signed consent form.

**7.3 Where will the original signed consent and PHI authorization documents be stored?**

Locked file cabinet in the office of the PI.

**7.4 Acknowledgement of consent form storage.**

 I will store original signed consent and/or PHI authorization documents for at least 6 years past the time the study is concluded.
 For studies involving minors, I will store original signed consent and/or PHI authorization documents for at least 6 years after the youngest participant turns 18.
 Not applicable – I am not collecting signed documents.

**8.0 Research and Data Collection Procedures:**

**8.1 Select the methods of data collection that will be used in this study (select all that apply):**

 Anthropometric measures (e.g., height, weight, waist circumference, etc.)	 Participant observation
--	--

# IRB Protocol for Human Subjects Research

 Audio/video recording	 Screening data
 Benign interventions	 Self-health monitoring (e.g., pedometers, food diaries, etc.)
 Biological specimens – blood draws	 Surveys – paper
 Biological specimens – clinically discarded blood or specimens	 Surveys – internet (including online and email-based data collection)
 Biological specimens (urine/feces, tissue, saliva, skin, hair, nails, nasal swab)	 Surveys – telephone
 Clinical Data Warehouse (CDW)	 Randomization with control and experimental groups
 Cognitive or behavioral measures, including daily diaries	 Records – billing
 Data collected using other communication/electronic devices (e.g., cell phones, pagers, and texting devices)	 Records – educational
 Data previously collected for research purposes	 Records – employee
 Deception	 Records – lab, pathology and/or radiology results
 Instrumentation, equipment, or software not approved by the FDA	 Records – mental health
 Interviews – focus groups	 Records – substance abuse
 Interviews – in person	 Research imaging protocols
 Interviews – virtual/online	 Recombinant DNA
 Medical records review	 Social networking sites
 MRI/ultrasound with contrast	 Stem cells
 MRI/ultrasound without contrast	 Radiation Scans (X-Ray, CT Scans, etc.)
 Non-invasive instruments (e.g., external sensors applied to the body)	 Other activities or interventions – describe: Investigators will obtain pain response scores (pain NRS, RASS, SERSDA), and monitor the subject at bedside

## 8.2 Description of research procedures.

Data to be abstracted from medical records include:

Demographic information

Age

# IRB Protocol for Human Subjects Research

Gender

History

Weight

PMH

Allergies

Home medications

Substance use

If yes what? alcohol, opioid, stimulant, hallucinogen, marijuana, tobacco

Clinical/treatment

HPI including time of bite, type of snake (if known), field treatments, ED treatment, vital signs, labs, imaging, medications administered and time (including analgesia), antivenom administration (time from bite to AV, type of AV, doses, and vials), procedures (i.e., splinting), measurements, adverse events, LOS

## Study specific data

Randomization drug (either ketamine or fentanyl)

### **Group A - Ketamine**

A single dose of ketamine 0.3 mg/kg IV over 15 minutes.

### **Group B - Fentanyl**

A single dose of fentanyl 1mcg/kg IV, maximum 100 mcg, over 15 minutes.

Time drug given

Data obtained prior to med administration and then following medication administration at intervals of 15, 30, 60 and 120 minutes

- Record vital signs (HR, B/P, resp rate, O2 sat)
- Obtain and assess pain response scores
  1. Pain Numerical Rating Score (NRS – 0-10)
  2. Richmond Agitation Sedation Scale (RASS)
  3. Side Effect Rating Scale for Dissociative Anesthesia (SERSDA)

The SERSDA score has been used in multiple studies to evaluate the side effects of ketamine [4].

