## 3.0 Purpose:

**Describe the purpose, specific aims, objectives, questions to be answered, hypotheses, and/or primary and secondary study endpoints of the Human Research.**

The purpose of this study is to evaluate differences in pain levels following a single administration of fentanyl or ketamine to treat pain after rattlesnake envenomation. The aim is to assess pain scores prior to medication administration, then 15, 30, 60, and 120 minutes after single medication administration. Primary endpoint is pain score at 30 minutes after medication administration. Secondary endpoints are pain scores at additional time points, need for rescue medication, adverse medication effects, and patient pain satisfaction scores at discharge.

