# IRB Protocol for Human Subjects Research

- Record any airway interventions required?  
If yes what? new supplemental O2/BVM/intubation, jaw thrust
- Record any rescue meds, dose and time

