#### **Group A - Ketamine**

A single dose of ketamine 0.3 mg/kg IV over 15 minutes.

Ketamine has been shown to be non-inferior in the treatment of multiple other painful conditions in similar hospital and emergency department settings. Ketamine has known side effects, including dysphoria, hypertension, and tachycardia, which are reduced when administered over 15 minutes compared to an intravenous push dose. Therefore, a 15-minute infusion will be used in the study. Ketamine is already commonly used for pain management within the hospital and carries a lowered risk of addiction compared to opiates such as fentanyl.

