#### **Group B - Fentanyl**

A single dose of fentanyl 1mcg/kg IV, maximum 100 mcg, over 15 minutes.

Fentanyl is a common opioid analgesic medication used for acute painful conditions. Fentanyl may cause respiratory depression, apnea, blurred vision, diaphoresis, dizziness, pruritis, urticaria, muscle rigidity, nausea, vomiting, and hypotension in high doses.

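### Most of the symptoms the protocol lists for fentanyl have no named scheduled question, while the only named side-effect scale targets dissociative effects, so the comparison of symptomatic side effects may be uneven

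*Combined protocol and SAP*

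**What the plan says.** Section 3.0 lists the secondary endpoints as pain scores at the other time points, "need for rescue medication, adverse medication effects, and patient pain satisfaction scores at discharge". No definition, summary measure or test is given for adverse medication effects. The Statistical Methods cover only the pain comparison.

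Section 8.2 sets out what is collected before the study drug and at 15, 30, 60 and 120 minutes after it, identically in both arms:

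- "Record vital signs (HR, B/P, resp rate, O2 sat"
- "Richmond Agitation Sedation Scale (RASS"
- "Side Effect Rating Scale for Dissociative Anesthesia (SERSDA"
- "Record any airway interventions required", with a short list of possible interventions

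The reason given for SERSDA, here and again in section 12.5, is that "The SERSDA score has been used in multiple studies to evaluate the side effects of ketamine [4". No comparable scale or symptom list is named for opioid effects. Other adverse events appear in section 8.2 as one entry among the data taken from the medical record. Section 13.3 adds general adverse-event monitoring by investigators.

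Section 10.1 then names the effects expected of each drug. For ketamine: "Ketamine has known side effects, including dysphoria, hypertension, and tachycardia". For fentanyl: "Fentanyl may cause respiratory depression, apnea, blurred vision, diaphoresis, dizziness, pruritis, urticaria, muscle rigidity, nausea, vomiting, and hypotension in high doses".

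**The concern.** The plan compares two drugs with different side-effect profiles and names the effects it expects from each. The one scale that rates side effects is built around one drug's characteristic effects. Most of the symptoms listed for the other drug have no named question.

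Symptoms asked about at fixed times are generally recorded more completely than symptoms left to be noticed or charted. If dissociative symptoms are prompted and itching or vomiting is not, a total of side effects mixes well-captured and poorly captured events.

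This matters because sections 1.0 and 2.0 present ketamine as a safe and effective non-opioid option, so tolerability is part of what readers will take from the trial. The Group Size Calculations section says the results may be used to plan a larger study, and a gap in the data form could carry over into it. Symptoms not asked about at the bedside cannot be recovered at analysis.

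**Working it through.** The plan states no figure on this point, so there is none to reproduce. Two checks were made.

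**1. Effects listed in section 10.1 against the scheduled measures in section 8.2**

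| Effect listed for fentanyl | Named scheduled measure |
|---|---|
| Respiratory depression | Respiratory rate, O2 saturation, airway items |
| Apnea | Respiratory rate, O2 saturation, airway items |
| Hypotension | Blood pressure |
| Nausea | None, unless in SERSDA |
| Vomiting | None, unless in SERSDA |
| Pruritus | None, unless in SERSDA |
| Urticaria | None, unless in SERSDA |
| Dizziness | None, unless in SERSDA |
| Diaphoresis | None, unless in SERSDA |
| Blurred vision | None, unless in SERSDA |
| Muscle rigidity | None, unless in SERSDA |

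The count is 11 listed, 3 covered and 11 − 3 = 8 without a named item. If SERSDA is assumed to include nausea, dizziness and vision, 8 − 3 = 5 remain: vomiting, pruritus, urticaria, diaphoresis and muscle rigidity.

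The opening paragraph of section 10.1 pools 17 effects across the study drugs and leads to the same place:

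- RASS and vital signs cover 7: sedation, respiratory depression, apnea, bradycardia, tachycardia, hypertension and hypotension.
- Laryngospasm would be reached through the airway items if it needed an intervention.
- Dysphoria could be reached only through SERSDA.
- That leaves 17 − 7 − 1 − 1 = 8, the same eight symptoms.

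**2. What uneven capture would do**

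Let s_D be the share of dissociative symptoms that is recorded and s_O the share of opioid-type symptoms. Because the instruments are the same in both arms, take each share as equal across arms. Let ΔD be the true excess of dissociative symptoms on ketamine, and ΔO the true excess of opioid-type symptoms on fentanyl.

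- For one opioid-type symptom, the recorded difference is s_O × ΔO. It shrinks toward zero but does not reverse.
- For a pooled count, the recorded difference (ketamine minus fentanyl) is s_D × ΔD − s_O × ΔO.
- With even capture at s_D it would be s_D × (ΔD − ΔO).
- The shift is therefore (s_D − s_O) × ΔO.

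The shift counts against ketamine only if s_D exceeds s_O and ΔO is positive. It is zero if the two types of symptom are captured equally well. The documents give none of s_D, s_O, ΔD or ΔO, so no size can be put on it.

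Two features of the plan affect these terms. Fentanyl is also the rescue drug and section 2.0 leaves other analgesics unrestricted, so opioid symptoms can occur in the ketamine arm and make ΔO smaller. The Randomization section blinds subjects but does not say that investigators are blinded, and investigators randomise, score and abstract. Unprompted recording could then differ by arm as well as by symptom, in either direction.

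**The case against.** The strongest reply is that ascertainment is the same in both arms. RASS, SERSDA, vital signs and airway items are collected at the same times whichever drug is given, and they capture the opioid effects that matter most for safety. Investigators are medical toxicologists at the bedside, who can see vomiting, urticaria, sweating or rigidity. The SERSDA items are not shown, and section 12.5 refers to a data form that is not in the documents and might already prompt for symptoms. This is a 40-subject pilot with no test planned for adverse effects.

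Much of that stands, and it rules out several stronger readings:

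- A reader might infer that SERSDA is the only active capture of side effects. It is the only named side-effect scale, but not the only structured capture.
- A reader might infer that fentanyl effects are in fact under-counted and the comparison is in fact tilted against ketamine. The documents do not show this. Any imbalance is by symptom type, and it would vanish if the eight symptoms were captured as well as the dissociative ones.
- A reader might set the proportion of ketamine effects covered against the proportion for fentanyl. That contrast is unsound. Dysphoria counts as covered only if SERSDA is credited with an unseen item, while no such credit is given on the fentanyl side. The ketamine list is also openly partial.

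What the reply does not remove is that the plan lists eight symptoms and names no scheduled question for them. Being at the bedside is not the same as asking: pruritus, nausea, dizziness and blurred vision are known mainly from the patient. The absence of a planned test means that the endpoint is undefined as well, not that its collection is sound.

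**Conclusion.** The point holds as a gap in data collection, not as a demonstrated bias. Eight of the 11 effects listed for fentanyl have no named scheduled item, or five if SERSDA is assumed to cover nausea, dizziness and vision. The comparison of symptomatic side effects may therefore be unbalanced by symptom type, and a pooled count could make ketamine look relatively worse. The scheduled capture of sedation, respiratory, haemodynamic and airway effects is not in question.

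The conclusion rests on two assumptions: that SERSDA does not contain most of these symptoms, and that the separate data form has no prompts for them. If either is wrong, the gap narrows or closes, and the remedy is to say so in section 8.2. The change is worth making before enrolment because the missing information cannot be collected afterwards.

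**What to change.** In section 8.2, where the assessments at each time point are listed:

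1. State the SERSDA items.
2. Add a short yes/no checklist of the symptoms in section 10.1 that SERSDA and vital signs do not already cover. It should include at least pruritus, urticaria, diaphoresis, muscle rigidity and vomiting, plus nausea, dizziness and blurred vision if SERSDA does not ask about them.
3. Ask it in the same words in both arms at 0, 15, 30, 60 and 120 minutes.
4. Define the endpoint as effects new or worse than time zero. Section 10.1 notes that antivenom can cause allergic reactions, so itching or urticaria cannot be interpreted without a baseline.
5. Report SERSDA separately, as a measure of dissociative effects.

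The cost is 5 to 8 yes/no items at five assessments, which is 25 to 40 short questions per subject. They should fit the 10 minutes that section 8.3 allots to each assessment, although that slot also holds the NRS, RASS, SERSDA and vital signs, so a dry run is sensible. No extra staff, visit or procedure is needed. The downside is that more minor events will be recorded in both arms.

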# IRB Protocol for Human Subjects Research

- Record any airway interventions required?  
If yes what? new supplemental O2/BVM/intubation, jaw thrust
- Record any rescue meds, dose and time

## Rescue medication - Fentanyl

1 mcg/kg IV fentanyl (0.5 mcg/kg if age >55 yrs)

Defined as rescue if given <30 min post study intervention for pain score >5 or patient requesting additional medication.

Patient pain satisfaction score at discharge

## Instrument Administration

Patients meeting inclusion criteria will be identified by the study investigators who are BUMCP physician medical toxicologists and care for RSEs. Informed consent, randomization and data abstraction/collection will be obtained by the investigators. Pain scores will be obtained at bedside by investigators at the following intervals; prior to medication administration (zero) and after medication administration at the following intervals 15, 30, 60, and 120 minutes, and a patient satisfaction score at discharge.

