## Randomization

Block randomization – A randomization list has been developed that will be used to assign drug (form: ‘Master List-Randomization’). Following enrollment, the subject will be assigned in sequential order. Each block will alternate between each drug (ketamine or fentanyl). Subjects will have 50/50 chance of being assigned to ketamine or fentanyl and will be blinded to which drug they received during the study. After participation in study (meaning they have completed their patient satisfaction score at discharge) subjects will be told what medication they received during the study.

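### Only the subject is blinded, and nothing in the plan keeps the investigators who score pain, sedation and side effects from knowing the arm

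*Combined protocol and SAP*

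**What the plan says.** Under Instrument Administration (Section 8.2), "Informed consent, randomization and data abstraction/collection will be obtained by the investigators", and "Pain scores will be obtained at bedside by investigators" before the drug and at 15, 30, 60 and 120 minutes. The checklist in Section 8.1 extends this to all three instruments: "Investigators will obtain pain response scores (pain NRS, RASS, SERSDA), and monitor the subject at bedside". Section 12.5 repeats these roles.

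The investigators are also the treating doctors. Section 8.2 describes them as "study investigators who are BUMCP physician medical toxicologists and care for RSEs". The randomized drug is listed under Study specific data, among the items they collect.

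On masking, the Randomization paragraph says that subjects "will be blinded to which drug they received during the study", and that they are told the drug after the discharge satisfaction score. No other role is mentioned.

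**The concern.** One group holds the assignment list, treats the patient, asks for the pain score, rates sedation, collects side effects and records rescue. If the person at the bedside knows the drug, the way a 0-10 score is prompted, rounded or written down can differ between arms. A rater who knows that ketamine was given may also look harder for dissociation. This is separate from whether the next assignment can be predicted: a concealed, properly random list would still leave the scorer free to know the drug once it had been assigned.

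Such bias does not shrink with sample size. Group Size Calculations says the results may be used to plan a larger study, so a distorted estimate would carry forward. The direction is not known. A drift toward similar scores would favour the stated hypothesis of no difference (Section 3.0).

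**Working it through.** The plan states no figure on this point, so the main check is a reading of the text.

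**Who does what, and who is masked**

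| Step | Who | Where | Masking stated |
|---|---|---|---|
| Consent, randomization, data collection | Investigators | 8.2 Instrument Administration, 12.5 | None |
| NRS: subject's rating, obtained at bedside | Investigators | 8.1, 8.2, 12.5 | Subject only |
| RASS: observer's rating | Investigators | 8.1, 8.2, 12.5 | None for the rater |
| SERSDA | Investigators | 8.1, 8.2, 12.5 | Subject only |
| Bedside and safety monitoring | Investigators | 8.1, 10.2, 13.3 | None |

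The available text mentions no masked assessor, no preparation of the infusions by a third party, no neutral label, and no rule that the person who opens an assignment leaves the scoring of that subject to someone else. Both arms do receive one infusion over 15 minutes, which helps to keep the subject blinded.

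**How exposed each outcome is**

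- *Primary endpoint (pain score at 30 minutes, Section 3.0).* The subject gives the number and is blinded. Bias needs an indirect route: elicitation, rounding, or a cue that unmasks the subject.
- *Rescue.* Section 8.2 ties it to a pain score above 5 or a request by the patient. Both start with the blinded subject, so exposure is again indirect.
- *RASS.* The observer rates it, so it is directly exposed. Section 3.0 does not name it as an endpoint and Statistical Methods plans no test of it. It bears at most on adverse effects.
- *Adverse medication effects.* A named secondary endpoint. It depends partly on what the investigator asks and notices.

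**Illustration of size**

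From the documents: 40 subjects in a 50/50 split, taken as n = 20 per arm, and a two-sided alpha of 0.05. Assumed, with no source in the documents: a shift b between arms caused by scoring, and an SD of the change in NRS. The model is a two-sample t-test with no true difference. It stands in for the Wilcoxon test that the plan names, so its figures are approximate for the planned analysis.

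- Standard error = SD × √(2/20). At SD 2.5 this is 2.5 × 0.316 = 0.791.
- Noncentrality = b / SE, on 38 degrees of freedom. The two-sided critical value is 2.024.
- Rejection probability = P(T > 2.024) + P(T < −2.024) under the noncentral t.

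| SD | Shift b | b / SE | Chance of p < 0.05 |
|---|---|---|---|
| 2.5 | 0 | 0 | 5.0% |
| 2.5 | 0.3 | 0.379 | 6.6% |
| 2.5 | 0.5 | 0.632 | 9.5% |
| 2.5 | 0.8 | 1.012 | 16.7% |
| 2.0 | 0.5 | 0.791 | 12.0% |
| 3.0 | 0.5 | 0.527 | 8.1% |

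These figures show what a shift of a given size would do. They do not show that such a shift would occur.

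**The case against.** The strongest reply is that the documents never say that investigators are unblinded, nor that one individual both randomizes and scores the same subject. Tasks are given to the investigators as a group, and the randomization form and data collection form are not part of the text. A reader might infer that outcomes are collected with knowledge of the arm. That goes further than the text. What stands is that nothing in the plan prevents it.

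A reader might also infer that the primary result is biased. The documents do not support this either: the NRS comes from a blinded subject. Nor is rescue directly exposed, because both triggers come from the subject.

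The magnitude is fairly criticised as assumed throughout. Statistical Methods also has a second criterion, a difference above 1.3 points with a 95% confidence interval. If that means the whole interval must lie beyond 1.3 (the wording is unclear), the same t model gives a false claim in at most about 0.7% of trials for shifts of 0.3 to 0.8 and SDs of 2 to 3. The inflation therefore concerns the p-value, and much less a claim of clinical difference read in that strict way.

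Finally, single-blind is a recognised design for an unfunded, single-centre pilot of 40. Masking the scorer also has limits here: Section 5.0 gives no number of investigators, and the people to be masked also monitor safety. These points stand. They narrow the remedy, but they do not argue against having subjects record their own scores, which needs no extra staff.

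**Conclusion.** The point holds in a limited form. The plan blinds the subject alone, gives randomization, care and all bedside scoring to the investigators, and has no safeguard against a scorer knowing the arm. For the primary NRS the risk is indirect; for RASS and adverse effects it is more direct. That a scorer knows the arm is inferred from the shared roles, the recorded drug and the silence on everyone except the subject. The title pages are not in the available text, so a masking statement there cannot be excluded.

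The size is unknown. The range of about 7% to 17% rests on an assumed shift of 0.3 to 0.8 points, SD 2.5, 20 per arm and a t-test, and should not be read as an estimate of this trial's error rate. The change is worth making because it costs little and protects the primary endpoint, not because bias has been shown.

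**What to change.** In Instrument Administration, add:

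1. At each time point the subject records the NRS and SERSDA answers in reply to a fixed script, before any discussion with the investigator. A subject who cannot write points to the answer or states it in reply to the same script. The answer is entered verbatim.
2. Where two of the existing investigators are present, the one who opens the assignment does not score that subject, provided that drug identity stays immediately available for safety care.
3. Where this is not possible, describe the trial as single-blind and report RASS and adverse effects as unmasked assessments.

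The cost is a paper form and some scheduling. The paper survey box in Section 8.1 is unchecked, so the data collection methods would need an update with the IRB. Some subjects will not be able to write because of a splinted limb, or because of the sedation, dizziness or blurred vision listed in Section 10.1, possibly unequally by arm. The pointing or spoken reply covers them, and the form should record which mode was used. No dose, rescue rule or other part of care changes.
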